4.4 Secondary Outcome 2: Participant Satisfaction

Participants will rate their satisfaction with their experience using virtual reality during colonoscopy on a numeric rating scale of 1-10 (1 = not satisfied, 10 = extremely satisfied). This data will be collected immediately following the colonoscopy.

4.5 Secondary Outcome 3: Participant Willingness to Undergo Future Colonoscopies With Virtual Reality and no Pharmacological Sedation

Participants will rate their willingness to undergo future colonoscopies using virtual reality and no-pharmacological sedation as "Yes," "Maybe," or "No." This data will be collected immediately following the colonoscopy.

4.6 Secondary Outcome 4: Endoscopist Satisfaction

Endoscopists will rate their satisfaction performing colonoscopy on participants using virtual reality instead of pharmacological sedation on a numeric rating scale of 1-10 (1 = not satisfied, 10 = extremely satisfied). This data will be collected immediately following the colonoscopy.

4.7 Secondary Outcome 5: Endoscopist Willingness to Incorporate Virtual Reality Into Regular Colonoscopy Practice

Endoscopists will indicate whether they would incorporate VR into their regular colonoscopy practice by selecting one of the following: "Yes" "No" or "Yes, but I would use virtual reality as an adjunct therapy rather than a standalone therapy." This data will be collected immediately following the colonoscopy.

5. Populations to be analyzed

The population analyzed will consist of all participants who initiate the study using the virtual reality technology.

6. Analyses

6.1 Primary Outcome 1: Proportion of Participants Who Complete Colonoscopy Using Virtual Reality and no Pharmacological Rescue

This outcome will be analyzed as a percent from the proportion of participants who complete colonoscopy using VR and no pharmacological rescue.

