## **IV. Subject Enrollment**

Adult patients (over the age of 18) who have a scheduled screening or surveillance colonoscopy and have undergone at least one prior colonoscopy will be eligible for recruitment. The electronic medical record of the potential subject may be reviewed prior to contacting the patient to confirm eligibility status. Once a potential subject is identified, the patient will be sent a mailing which will outline the study, and request the opportunity for the research coordinator to contact them by phone regarding the study. This letter will provide the phone number of the research coordinator, and patients will be asked to contact the coordinator if they wish to participate. If the patient has not contacted the research coordinator two weeks after the letter has been sent, the coordinator will contact potential subjects by phone. A disclaimer on the letter will be included stating this. If the subject declines to take part in the

study, his/her name will be removed from the mailing list and they will not be contacted again regarding this research.

**Recruitment group:** Patient contacts research coordinator regarding study via phone

If the patient calls the research coordinator after receiving the letter in the mail, the coordinator will explain the study using a call script.

**Recruitment group:** Patient does not contact research coordinator after letter has been sent

If the patient does not contact the research coordinator following the mailing, the coordinator will contact him/her by telephone to explain the study using the call script and answer any questions. One phone call attempt will be made; if there is no response, the patient will not be contacted further.

All participants will be required to sign the written informed consent form on the day of the procedure.

The consent form will be pre-mailed to participants at their request.

**Patient recruitment targets:** This is a pilot study meant to assess effectiveness of a virtual reality approach to pain management. We aim to recruit 25 participants that are coming for routine screening or surveillance colonoscopies at MGH.

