Statistical Analysis Plan

Virtual Reality Alternative to Pharmacological Sedation During Colonoscopy

Principal Investigator

[name]

Director, High-Risk GI Cancer Clinic

Massachusetts General Hospital

Boston, Massachusetts

Protocol Identification Number

2018P001618

ClinicalTrials.gov identifier

[figure not shown]
NCT04349150

Statistical Analysis Plan

Virtual Reality Alternative to Pharmacological Sedation During Colonoscopy

Signature Page

Principal Investigator

[name]

9-22-2021

Date

1. Introduction

Virtual reality (VR) technology has been previously explored to reduce pain perception during medical procedures through distraction. We sought to determine whether VR technology may be a feasible alternative to pharmacological sedation during colonoscopy procedures.

2. Study design

Individuals 18 years or older who are scheduled for a routine colonoscopy and who have had a prior colonoscopy will be recruited to participate. The recruitment goal for this pilot study is 30 participants. Study participants will prep for the colonoscopy according to standard practice and will be prepared for the colonoscopy according to the standard of care at Massachusetts General Hospital. All participants will undergo a VR experience through a head-mounted display (HMD) throughout the duration of the colonoscopy and the procedure will be initiated without the administration of IV sedatives or narcotics. However, standard pain medication will be available upon participant request.

All participants will be asked to complete a questionnaire about their experience. The endoscopist will also complete a questionnaire about their experience working with the participant using VR distraction.

3. Aims and objectives

The goal of the study is to assess whether VR is an acceptable alternative to using pharmacological sedation during colonoscopy procedures. Data will be collected on participant willingness, tolerability, experience, and desire to use VR during subsequent colonoscopies.

4. Outcomes

4.1 Primary Outcome 1: Proportion of Individuals Who Complete Colonoscopy Using Virtual Reality and no Pharmacological Rescue

This outcome will be measured as x/n , where x = number of participants who completed colonoscopy using virtual reality and no pharmacological rescue, and n = total number of participants who initiated colonoscopy using virtual reality. This data will be collected immediately following the colonoscopy.

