6.2 Primary Outcome 2: Cecal Intubation Rate

This outcome will be analyzed as a percent from the proportion of participants in whom cecal intubation is achieved.

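### Both primary proportions are to be reported as a bare percent, with no confidence interval, on about 25 to 30 participants at most

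*SAP*

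**What the plan says.** SAP 4.1 and 4.2 define the two primary outcomes as fractions x/n. The numerators are, respectively, participants who finish the colonoscopy on VR without drug rescue and those whose cecum is reached on VR without sedation. Both fractions share one denominator: "n = total number of participants who initiated colonoscopy using virtual reality". SAP 5 sets the analysis population in similar terms: "The population analyzed will consist of all participants who initiate the study using the virtual reality technology".

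The analysis of each primary outcome is a single sentence:

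- SAP 6.1: "This outcome will be analyzed as a percent from the proportion of participants who complete colonoscopy using VR and no pharmacological rescue".
- SAP 6.2: "This outcome will be analyzed as a percent from the proportion of participants in whom cecal intubation is achieved".

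The planned size is stated twice, with different values. SAP 2 says "The recruitment goal for this pilot study is 30 participants", and Protocol IV says "We aim to recruit 25 participants that are coming for routine screening or surveillance colonoscopies at MGH". Neither figure comes with an expected rate or a precision target. The purpose is given in SAP 3: "The goal of the study is to assess whether VR is an acceptable alternative to using pharmacological sedation during colonoscopy procedures". Protocol II adds that the data will support a conclusion and decisions on further research.

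**The concern.** Followed as written, the plan yields two primary results with no statement of how precisely they are known. The protocol has no statistical section, and no interval, standard error, test, benchmark or threshold for these outcomes appears in either document.

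A single-arm pilot does not need a hypothesis test. But where no test is planned, the interval is the natural place to show precision. The study also intends to say something about patients beyond those enrolled, namely whether VR is acceptable in place of sedation and what research should follow. With about 25 to 30 participants, the same percent can be compatible with quite different views of acceptability, and a reader would have to reconstruct that range.

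The plan is also uneven. The numeric secondary outcomes (SAP 6.3, 6.4 and 6.6) at least have a standard deviation beside the mean. That describes spread, not the precision of the estimate, but the primary outcomes have nothing beside the percent.

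**Working it through.** **Inputs from the documents**
- n up to about 25 (Protocol IV) or about 30 (SAP 2). Both are recruitment goals. The denominator can be smaller, because it counts only those who start with VR.
- Planned output: a percent (SAP 6.1, 6.2).
- There is no sample-size or precision calculation in the plan, so there is no figure of its own to reproduce.

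**Assumptions**
- Two-sided 95% level.
- Observed rates from about 50% to 100%. The documents give none, so a range is shown.

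**Formulas**
- Clopper-Pearson (exact): lower limit = the 0.025 quantile of Beta(x, n − x + 1); upper limit = the 0.975 quantile of Beta(x + 1, n − x). When x = n the upper limit is 1 and the lower limit reduces to 0.025^(1/n).
- Wilson, with p = x/n and z = 1.96: centre = (p + z²/2n)/(1 + z²/n); half-width = z·√(p(1 − p)/n + z²/4n²)/(1 + z²/n).

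**Worked cases**
- 24/30, exact: the 0.025 quantile of Beta(24, 7) is 61.4% and the 0.975 quantile of Beta(25, 6) is 92.3%. Width 92.3 − 61.4 = 30.9 points.
- 24/30, Wilson: centre 76.6%, half-width 13.9 points, giving 62.7–90.5% (width 27.8).
- 25/25, exact: lower limit 0.025^(1/25) = 86.3%.
- 30/30, exact: lower limit 0.025^(1/30) = 88.4%.

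**Results** (widths in percentage points, computed before rounding the limits)

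| Observed | Percent | Exact 95% interval | Exact width | Wilson width |
|---|---|---|---|---|
| 13/25 | 52.0 | 31.3–72.2% | 40.9 | 36.5 |
| 20/25 | 80.0 | 59.3–93.2% | 33.9 | 30.3 |
| 22/25 | 88.0 | 68.8–97.5% | 28.7 | 25.8 |
| 24/25 | 96.0 | 79.6–99.9% | 20.3 | 18.8 |
| 25/25 | 100 | 86.3–100% | 13.7 | 13.3 |
| 15/30 | 50.0 | 31.3–68.7% | 37.4 | 33.7 |
| 24/30 | 80.0 | 61.4–92.3% | 30.9 | 27.8 |
| 27/30 | 90.0 | 73.5–97.9% | 24.4 | 22.2 |
| 29/30 | 96.7 | 82.8–99.9% | 17.1 | 16.1 |
| 30/30 | 100 | 88.4–100% | 11.6 | 11.4 |

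The widest exact interval for any x is 40.9 points at n = 25 and 37.4 points at n = 30. An observed 80% is therefore compatible with a true completion rate of roughly three in five or of more than nine in ten. The choice between 25 and 30 shifts the width by only 2 to 4 points in these rows, so the point holds at either target.

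**The case against.** The best case for the plan is that this is a descriptive pilot. It has one arm, no comparator and no success threshold, so no decision rule would change if an interval were added. The percent itself is not biased. The outcomes are defined as x/n, so anyone given both counts can compute the interval, and nothing in the SAP forbids reporting one. An interval also covers sampling error only. It says nothing about selection, and the participants here are volunteers at one hospital who have already had a colonoscopy.

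Much of this is true and limits the weight of the point. The omission makes the reporting incomplete; it does not make the estimate wrong. The interval is not the sole way to convey precision, since a standard error or the two counts would do part of the work. The figures 25 and 30 are goals and not caps, and the size of the effect depends on a rate not yet known from the documents.

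It does not remove the point. SAP 6.1 and 6.2 promise only a percent, so the plan does not guarantee that x and n will be printed. Naming the method in advance also settles a real, if modest, choice (30.9 against 27.8 points at 24/30). With no threshold to refer to, a reader judging acceptability needs the range more, not less.

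**Conclusion.** The concern holds. Both primary outcomes are planned as a percent alone, and at either target size the uncertainty left unstated is large: 31 to 41 points of full width for observed rates of about 50–80%, 24 to 29 near 88–90%, 17 to 20 near 96–97%, and 12 to 14 at 100%. Wilson intervals are somewhat narrower (28–37, 22–26, 16–19 and 11–13 points) and lead to the same conclusion.

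These figures rest on the 95% level, on the assumed observed rates, and on every recruited participant starting with VR. A smaller denominator would generally widen the intervals. This should be corrected. It does not bias the estimates, but it affects both primary results and is cheap to put right.

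**What to change.** Add to each of SAP 6.1 and 6.2: *The result will be reported as x/n, the percent, and a two-sided 95% Clopper-Pearson confidence interval.* Wilson is an acceptable alternative if it is the method named in advance.

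In 6.2, let the sentence refer back to the x and n of SAP 4.2. The wording of 6.2 alone does not repeat that intubation counts only when reached on VR without sedation, and the interval should clearly belong to that fraction.

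State the feasibility conclusion with the estimate and the whole interval together. The lower limit should not stand in for the estimate.

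The cost is one sentence per section and no new data or participants. The reported result will look less precise, and the exact interval is a little wider than Wilson. The two recruitment targets (25 and 30) should be reconciled separately; this change does not depend on which is kept.

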6.2 Primary Outcome 2: Cecal Intubation Rate

This outcome will be analyzed as a percent from the proportion of participants in whom cecal intubation is achieved.

6.3 Secondary Outcome 1: Participant-reported Pain and Discomfort Levels

The mean values for participants' pain and discomfort will be calculated, along with the standard deviation.

6.4 Secondary Outcome 2: Participant Satisfaction

The mean values for participant satisfaction will be calculated, along with the standard deviation. Correlation between satisfaction values and values for pain and discomfort will be assessed using the Pearson r correlation.

6.5 Secondary Outcome 3: Participant Willingness to Undergo Future Colonoscopies With Virtual Reality and no Pharmacological Sedation

Counts of participants selecting “Yes,” “Maybe,” and “No” will be analyzed as percentages.

6.6 Secondary Outcome 4: Endoscopist Satisfaction

The mean values for endoscopist satisfaction will be calculated, along with the standard deviation.

6.7 Secondary Outcome 5: Endoscopist Willingness to Incorporate Virtual Reality Into Regular Colonoscopy Practice

Counts of endoscopists selecting “Yes,” “No,” and “Yes, but I would use virtual reality as an adjunct therapy rather than a standalone therapy” will be analyzed as percentages.

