## V. Study Procedures

Researchers will collect data from the electronic medical records of patients on relevant medical history that might affect the colonoscopy, such as history of prior abdominal surgery, infection, or peritonitis.

If the patient agrees to participate prior to the procedure, the research coordinator will meet the subject at his/her colonoscopy appointment. The research coordinator will review the study procedures, answer any remaining questions, and obtain written informed consent using the written informed consent form. The subject will then be prepped for his/her colonoscopy by a registered nurse, and standard colonoscopy consent including consent to pharmacological sedation will be obtained by the endoscopist.

Once inside the procedure room, the research coordinator will fit the consented participant with a virtual reality head-mounted display (HMD), and set up virtual experiences for the patient to go through during their procedure through a control tablet. The HMD will completely obscure the patient's sight of the real room. The virtual environment will be enhanced with sound effects from the HMD, but the participant will still be able to hear the sounds of the procedure room so that they may respond to the verbal requests of their clinicians. The colonoscopy will proceed according to standard practice using virtual reality instead of chemical analgesics for as long as the participant chooses.

Should a participant who consented to drug administration prior to the procedure request pain medication, the research coordinator will remove the HMD and a registered nurse will administer the appropriate medications, following the standard of care at MGH.

All subjects will be asked to complete a questionnaire about their experience regardless of whether pain medication was requested. The questionnaire will collect subjective data on patient experience. The research coordinator will complete a case report form with objective data about the procedure, including duration of colonoscopy, total time spent without sedation, and events and complications during the procedure as noted by the physician. Finally, the endoscopist will also complete a brief questionnaire about his/her experience working with the patient using virtual reality distraction.

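### Does SAP 6.7 need a stated unit and denominator before its percentages of endoscopists can be reported?

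*SAP*

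**What the plan says.** Three places fix how the endoscopist's answers are collected.

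- Protocol section V (Study Procedures) says that "the endoscopist will also complete a brief questionnaire about his/her experience working with the patient using virtual reality distraction".
- SAP section 2 repeats this: "The endoscopist will also complete a questionnaire about their experience working with the participant using VR distraction".
- SAP 4.7 defines the outcome: "Endoscopists will indicate whether they would incorporate VR into their regular colonoscopy practice by selecting one of the following" three options (yes, no, or yes as an adjunct only). It adds "This data will be collected immediately following the colonoscopy".

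Two places bear on the analysis.

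- SAP 6.7 takes "Counts of endoscopists selecting" each option and turns the counts into percentages.
- SAP section 5 gives the only analysis set: "The population analyzed will consist of all participants who initiate the study using the virtual reality technology".

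The companion outcome in SAP 6.6, from the same endoscopists at the same moment, reads "The mean values for endoscopist satisfaction will be calculated, along with the standard deviation".

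Neither document gives the number of endoscopists, says whether one may perform several study procedures, or says how differing answers from one endoscopist are combined.

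**The concern.** The unit of collection and the unit of reporting do not obviously match. The form is completed about one patient, straight after that patient's procedure, so the natural expectation is one form per participant. The question, however, concerns the endoscopist's usual practice, which belongs to the doctor and not to the case. The result is then labelled as a count of endoscopists.

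If forms are counted, an endoscopist with many cases weighs more than one with few, and a percentage of procedures could be read as a percentage of doctors. If doctors are counted, someone must decide what to do when a doctor's answer changes from case to case, and the SAP leaves that decision open until the answers are known. Since 6.7 is the only planned result on whether endoscopists would adopt virtual reality, an ambiguous denominator looks like a defect in the whole of that result.

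**Working it through.** The plan states no figure for this outcome, so there is nothing to reproduce. The check asks how far the two readings can diverge, and whether anything in the plan depends on which one is used.

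**Inputs from the documents.** The number of forms n is at most 25 (Protocol section IV recruitment target) or 30 (SAP section 2 recruitment goal). That difference is a separate matter.

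**Inputs assumed.** The number of endoscopists k, each one's caseload, and the pattern of answers. The documents give none of these.

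**Divergence.** Suppose one endoscopist with m of the n forms always answers Yes and nobody else does. Then

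- percentage by form = m/n
- percentage by endoscopist = 1/k

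With k = 5 the second is 1/5 = 20% throughout.

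| n | m | By form | By endoscopist |
|---|---|---|---|
| 30 | 1 | 1/30 = 3.3% | 20% |
| 30 | 6 | 6/30 = 20.0% | 20% |
| 30 | 12 | 12/30 = 40.0% | 20% |
| 30 | 14 | 14/30 = 46.7% | 20% |
| 25 | 1 | 1/25 = 4.0% | 20% |
| 25 | 5 | 5/25 = 20.0% | 20% |
| 25 | 10 | 10/25 = 40.0% | 20% |
| 25 | 12 | 12/25 = 48.0% | 20% |

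A deliberately lopsided case goes further. With n = 30 and k = 3, where one endoscopist does 28 cases and the other two do one each, the result by form is 28/30 = 93.3% and by endoscopist 1/3 = 33.3%.

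**When they agree.** If each endoscopist does one case, n = k and the two are identical. If caseloads are equal and each endoscopist's answer is constant, with a of the k answering Yes, the result by form is a(n/k)/n = a/k, again identical. Divergence therefore needs repeat cases together with unequal caseloads or changing answers.

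**Changing answers.** If doctors are counted, one doctor whose answer changes moves a category by 1/k, depending on which answer is used: 33.3, 20.0 or 10.0 percentage points for k = 3, 5 or 10.

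**What depends on it.** SAP 6.7 plans percentages only. There is no confidence interval that within-doctor correlation could make too narrow, no test, and no cut-off for proceeding. The primary outcomes in SAP 4.1 and 4.2 have participants as numerator and denominator and do not use the endoscopist's form.

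**The two readings against the text.**

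- *Distinct endoscopists.* This is the literal sense of 6.7 and suits a question about regular practice. The denominator is then the number of endoscopists who answered.
- *Forms.* This follows from the per-patient form, the timing in 4.7 and the participant population in section 5. It treats 6.7 as parallel to 6.5, which counts participants' answers in the same way. The denominator is then the forms completed for that population.

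Each reading supplies its own denominator and a legitimate description. Neither yields a wrong number if its unit is named in the report.

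**The case for a change.** The best argument for a change is that when a percentage is the entire analysis, its denominator is the entire specification. The SAP writes out x and n for both primary outcomes, so it could have done so here. A reader told that 40% of endoscopists would adopt virtual reality will think of doctors, not procedures. One sentence written before the data are seen would also remove any freedom to choose the more favourable basis.

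The facts behind this stand: no denominator is written, and no rule covers repeated answers. The inference to harm is weaker. That the form is completed once per procedure is a fair inference from the wording and timing, but that any endoscopist has repeat cases is not stated anywhere. The questionnaire and case report form are not among the documents, so it cannot be said that the endoscopist's identity goes unrecorded. The argument also treats two like items differently if it accepts a per-procedure mean in 6.6 but rejects a per-procedure percentage in 6.7, since willingness too may reflect the case just finished.

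The obvious remedy, one answer per endoscopist taken after the last case, is a preference and not a correction. It drops most responses from the headline figure and leaves a small, coarse denominator. Reasonable statisticians would differ on it.

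**Conclusion.** The observation is accurate, but it describes missing detail and not an error. An analyst can fill it sensibly by naming the unit, printing the counts beside the percentages and saying how many endoscopists contributed. That is ordinary reporting practice and needs no amendment to the SAP.

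The possible size cannot be fixed from the documents. It is nil if each endoscopist does one case, or if caseloads are equal and answers constant. It is about 27 percentage points (46.7 − 20.0) in the moderate 30-form illustration and 60 points (93.3 − 33.3) in the lopsided one. These gaps follow from assumed caseloads and answers and are not evidence that this trial's result would shift. Even at their largest they would alter the label and weighting of the fifth of five secondary outcomes, with no inference or decision rule behind it. The conclusion rests on 6.7 staying descriptive, as it is written.
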